3. GENERAL STUDY DESIGN AND STUDY SCHEMATIC DIAGRAM

This is a multicenter, randomized, double-blind, parallel-group, placebo-controlled study with an open-label period to evaluate the efficacy, safety, and tolerability of monthly and quarterly sc fremanezumab compared with placebo in patients with CM and EM with inadequate response to prior preventive treatments.

The study will consist of a screening visit, a run-in period (28 days), a 12-week double-blind, placebo-controlled treatment period, a 12-week open-label period, and a follow-up visit 6.0 months after the last dose of fremanezumab for ADA blood sample collection.

At the end of the open-label treatment period (4 weeks after the last dose) an end of treatment study visit (visit 8) will be scheduled and patients should return to the care of their treating physicians. Patients should be treated with standard of care after withdrawal from or termination of the 24-week treatment period/study, as appropriate.

Double-blind period

At the baseline visit (visit 2), patients will be randomly assigned to a treatment group with fremanezumab (2 different dose regimens) or placebo in a 1:1:1 ratio as follows:

- For patients with CM:
 - sc administration of 675 mg of fremanezumab at visit 2 followed by monthly sc administration of 225 mg of fremanezumab for 2 months or
 - sc administration of 675 mg of fremanezumab at visit 2 followed by monthly sc administration of matching placebo for 2 months or
 - 3 monthly doses of matching placebo
- For patients with EM:
 - sc administration of fremanezumab at 225 mg plus 2 matching placebo injections as first dose followed by monthly sc administration of 225 mg of fremanezumab for 2 months or
 - sc administration of fremanezumab at 675 mg as first dose followed by monthly sc administration of matching placebo for 2 months or
 - 3 monthly doses of matching placebo

Randomization and treatment assignment for the double-blind period will be performed using electronic interactive response technology (IRT). The study will be stratified based on CM or EM, gender, country, and a special treatment failure group defined as patients who must have had inadequate response to valproic acid. In addition, patients in the special treatment failure group must have had inadequate response to 2 to 3 other classes of migraine preventive medications as defined in [Appendix H](#).

The proportion of CM and EM patients in the study should be approximately 50:50 in each subgroup.

CM is defined as:

Patient fulfills the following criteria for CM in prospectively collected baseline information during the 28-day run-in period:

- Headache occurring on ≥ 15 days
- On ≥ 8 days, fulfilling any of the following:
 - ICHD-3 diagnostic criteria C and D for 1.1 Migraine without aura ([Appendix U](#))
 - ICHD-3 criteria B and C for 1.2 Migraine with aura ([Appendix U](#))
 - Probable migraine (a migraine subtype where only 1 migraine criterion is missing)
 - The patient used a triptan or ergot derivative to treat established headache.

EM is defined as:

The patient fulfills the following criteria for EM in prospectively collected baseline information during the 28-day run-in period:

- Headache occurring ≥ 6 days but < 15
- On ≥ 4 days, fulfilling any of the following:
 - ICHD-3 diagnostic criteria C and D for 1.1 Migraine without aura
 - ICHD-3 criteria B and C for 1.2 Migraine with aura
 - Probable migraine (a migraine subtype where only 1 migraine criterion is missing)
 - The patient used a triptan or ergot derivative to treat an established headache

Blinded treatment will be administered sc once a month (approximately every 28 days) for a total of 3 doses (visits 2,3, and 4)

Open-label period

After visit 4, all patients completing the double-blind period will enter the open-label period. All patients (CM and EM) will receive sc 225 mg of fremanezumab monthly for 3 months (visits 5, 6, and 7).

The open-label period will not be randomized as all patients will receive the same monthly dose (225 mg fremanezumab).

Open-label treatment will administered for a total of 3 doses (visits 5, 6, and 7). Final study assessments will be performed at visit 8 (end-of-treatment [EOT] visit), approximately 4 weeks after administration of last dose of fremanezumab.

Follow up period

A follow-up visit will be scheduled 6.0 months (> 5 half-lives) after the last study drug administration for ADA blood sampling. Patients who discontinue early will have the follow-up visit 6.0 months after the last dose.

Clinical Study Protocol with Amendment 01

The total duration of patient participation in the study is planned to be 50 weeks including a run-in period lasting 28 days, a double-blind treatment period lasting 12 weeks, an open-label period lasting 12 weeks, and 1 follow-up visit at week 46.

[figure not shown]
Patients are expected to complete the entire duration of the study, including the open-label period and the follow-up visit.

The end of study is defined as the last visit of the last patient (follow-up visit, visit 9). However, an interim database lock will occur following the end of the double-blind treatment period of the last patient for analysis of that portion of the study data. A second interim lock will occur following the end of the open-label period.

[figure not shown]
The total study duration, including the 6.0-month follow-up-period, will be approximately 2 years (from approximately 4Q 2017 to 4 Q 2019).

The study schematic diagram for patients with CM is presented in [Figure 1](#) and for patients with EM in [Figure 2](#).

Figure 1: Overall Study Schematic Diagram for Patients with Chronic Migraine

EOT=end of treatment; PBO=placebo; V=visit.

Figure 2: Overall Study Schematic Diagram for Patients with Episodic Migraine

EOT=end of treatment; PBO=placebo; V=visit.

3.1. Planned Number of Patients and Countries

Approximately 804 patients (268 patients per treatment group) are planned to be enrolled in this study to have approximately 705 completers (235 completers per treatment group). A 12% drop-out rate is anticipated.

The study is planned to be conducted in approximately 15 countries in approximately 120 investigational centers.

3.2. Justification for Study Design and Selection of Population

The study population will be composed of female and male patients, aged 18 to 70 years, inclusive, with a history of migraine (as defined by International Classification of Headache Disorders, 3rd revision [ICHD-3] criteria [IHS 2013]) for at least 12 months prior to screening and diagnosis of EM and CM prospectively documented via a review of headache data recorded daily in an electronic headache diary device during a 28-day run-in period. In addition, patients need to have documented history of inadequate response to 2 to 4 classes of prior preventive medication treatments for migraine and a subset of patients (at least 120) will have documented inadequate response to 2 to 3 classes of prior preventive medications and in addition inadequate response to valproic acid. All inadequate responses must be within the past 10 years (in medical chart or by treating physician's confirmation, see [Appendix I](#)). Fremanezumab is expected to be a later line treatment in the EU. This study is intended to generate data for that specific population defined within EM and CM.

The same dosing regimens used in the phase 3 studies will be investigated in the double-blind period. One of the dosing regimens from the phase 3 studies expected to be efficacious for this study population will be used in the open-label period.

A randomized, double-blind, parallel-group, placebo-controlled design is appropriate given the objectives of this study. Furthermore, this design is consistent with the recommendations of the

Classifications Committee of the IHS for controlled trials of preventive drugs in migraine (Tfelt-Hansen et al 2012).

3.3. Stopping Rules for the Study

During the conduct of the study, serious adverse events will be reviewed (see Section 7.1.5) as they are reported from the investigational centers to identify safety concerns.

The study may be terminated by the sponsor for any reason at any time. For example, the sponsor should terminate the study in the event of:

- new toxicological or pharmacological findings or safety issues invalidating the earlier positive benefit-risk assessment
- development of the IMP being discontinued

A patient may discontinue participation in the study at any time for any reason (eg, lack of efficacy, consent withdrawn, or adverse event). The investigator and/or sponsor can withdraw a patient from the study at any time for any reason (eg, protocol deviation as defined in Appendix C, noncompliance, or adverse event). In addition, patients with positive eC-SSRS findings or abnormal hepatic laboratory values (eg, alanine aminotransferase [ALT], aspartate aminotransferase [AST], alkaline phosphatase [ALP], gamma-glutamyl transpeptidase [GGT], bilirubin [total, direct, or indirect], or international normalized ratio [INR]) may meet criteria for discontinuation from the IMP as summarized in Appendix R.

3.4. Schedule of Study Procedures and Assessments

Study procedures and assessments with their time points are presented in Table 2.

Note that blood samples for plasma drug concentration determination will be collected prior to dosing (where applicable) at visits 2, 3, 4, 5, 6, and 8.

Detailed descriptions of each method of procedures and assessments are provided in Section 6 (efficacy assessments), Section 7 (safety assessments), and Section 8 (pharmacokinetic and other assessments). Study procedures and assessments by visit are listed in Appendix B.

Table 2: Study Procedures and Assessments

Study period	Pretreatment (incl. screening visit and run-in period)	Double-blind treatment period			Open-label period				Follow up period
		V1	V2 ^a	V3	V4	V5	V6		
Day and allowed time windows	Screening (Days -28 to -1)	Month 0 (Day 0+3 days)	Month 1 (Day 28±3 days)	Month 2 (Day 56±3 days)	Month 3 (Day 84±3 days)	Month 4 (Day 112±5 days)	Month 5 (Day 140±5 days)	End of Treatment/ Early termination (Day 168±5 days)	6.0 months after the last dose of IMP (Day 320±15 days)
Procedures and assessments	Screening Week -4	Baseline Week 0	Week 4	Week 8	Week 12	Week 16	Week 20	Week 24	Week 46
Informed consent	X								
Inclusion and exclusion criteria	X	X							
Assign randomization/treatment number		X							
Medical and psychiatric history	X								
Record demographic characteristics	X								
Prior medication and treatment history ^b	X								
Clinical laboratory tests (serum chemistry, hematology and coagulation, urinalysis)	X	X	X		X	X		X	
Physical examination, including height and weight ^c	X	X			X			X	
12-Lead ECG ^d	X	X			X			X	
Vital signs measurement ^{e, f}	X	X	X	X	X	X	X	X	X

Study period	Pretreatment (incl. screening visit and run-in period)	Double-blind treatment period			Open-label period				Follow up period
		V1	V2 ^a	V3	V4	V5	V6		
Day and allowed time windows	Screening (Days -28 to -1)	Month 0 (Day 0±3 days)	Month 1 (Day 28±3 days)	Month 2 (Day 56±3 days)	Month 3 (Day 84±3 days)	Month 4 (Day 112±5 days)	Month 5 (Day 140±5 days)	End of Treatment/ Early termination (Day 168±5 days)	6.0 months after the last dose of IMP (Day 320±15 days)
Procedures and assessments	Screening Week -4	Baseline Week 0	Week 4	Week 8	Week 12	Week 16	Week 20	Week 24	Week 46
Serum β-HCG test ^g	X							X	
Urine pregnancy test ^g		X	X	X	X	X	X	X	
FSH ^h	X								
Inform patients of study restrictions and compliance requirements	X								
Review study compliance ^f		X	X	X	X	X	X	X	
Provide electronic headache diary ⁱ	X								
Complete electronic headache diary entries ^j	X							X	
Review electronic headache diary ^f		X	X	X	X	X	X	X	
Return headache diary device								X	
Blood samples for plasma concentration of IMP ^k		X	X	X	X	X		X	
Blood samples for serum ADA assessment ^l		X	X		X	X		X	X

Study period	Pretreatment (incl. screening visit and run-in period)	Double-blind treatment period			Open-label period				Follow up period
		V1	V2 ^a	V3	V4	V5	V6		
Day and allowed time windows	Screening (Days -28 to -1)	Month 0 (Day 0±3 days)	Month 1 (Day 28±3 days)	Month 2 (Day 56±3 days)	Month 3 (Day 84±3 days)	Month 4 (Day 112±5 days)	Month 5 (Day 140±5 days)	End of Treatment/ Early termination (Day 168±5 days)	6.0 months after the last dose of IMP (Day 320±15 days)
Procedures and assessments	Screening Week -4	Baseline Week 0	Week 4	Week 8	Week 12	Week 16	Week 20	Week 24	Week 46
Blood collection for serum, plasma, and RNA biomarker analysis		X	X		X	X		X	
Urine collection for biomarker analysis		X	X		X	X		X	
Saliva sample for biomarker analysis		X	X		X	X		X	
Blood samples for pharmacogenetics ^m		X							
HIT-6		X	X		X			X	
MIDAS		X	X		X			X	
PHQ-2/PHQ-9 ⁿ		X			X			X	
MSQOL questionnaire		X	X		X			X	
EQ-5D-5L questionnaire		X			X			X	
PGIC scale			X		X			X	
WPAI questionnaire		X			X			X	
eC-SSRS ^{o, f}	X		X	X	X	X	X	X	
Adverse events ^{g, p} and health care resource utilization inquiry		X	X	X	X	X	X	X	X
Administration of IMP		X	X	X	X	X	X		

Clinical Study Protocol with Amendment 01

Study period	Pretreatment (incl. screening visit and run-in period)	Double-blind treatment period			Open-label period				Follow up period
		V1	V2 ^a	V3	V4	V5	V6		
Day and allowed time windows	Screening (Days -28 to -1)	Month 0 (Day 0±3 days)	Month 1 (Day 28±3 days)	Month 2 (Day 56±3 days)	Month 3 (Day 84±3 days)	Month 4 (Day 112±5 days)	Month 5 (Day 140±5 days)	End of Treatment/ Early termination (Day 168±5 days)	6.0 months after the last dose of IMP (Day 320±15 days)
Procedures and assessments	Screening Week -4	Baseline Week 0	Week 4	Week 8	Week 12	Week 16	Week 20	Week 24	Week 46
Hypersensitivity/ Anaphylaxis ^g		X	X	X	X	X	X	X	
Concomitant medication inquiry ^f		X	X	X	X	X	X	X	X

^a All visit 2/baseline procedures must be performed before study drug administration and health care resource utilization inquiry. Inquiries about adverse events will be made before and after study drug administration. Post-dose inquiries will be made before the patient leaves the study center.

^b Collection of prior medications is limited to those medications administered within 6 months before study drug administration (visit 2) and preventive medications taken within 10 years.

^c Height will be measured only at the screening visit.

^d Electrocardiograms will be performed in triplicate. Procedure will be performed before other assessments (eg, blood draws and administration of questionnaires). The ECGs should be performed after the patient has been supine for at least 5 minutes.

^e Before pulse and blood pressure are measured, the patient must be in a supine or semi-erect/seated position and resting for at least 5 minutes. The same position and arm should be used each time vital signs are measured for a given patient.

^f Procedures for unscheduled visits.

^g Women of child bearing potential only.

^h Postmenopausal women only.

ⁱ Eligible patients will be given an electronic headache diary device and will be trained in its use and compliance requirements on the day of screening.

^j Patients will complete electronic headache diary entries about the previous day daily beginning on day -27 through the EOT/ early termination visit.

^k Blood samples for plasma drug concentration determination will be collected prior to dosing (as applicable) at visits 2, 3, 4, 5, 6, and 8.

^l Blood samples for serum ADA assessment will be collected prior to dosing (as applicable) at visits 2, 3, 5, 6, 8, and 9 and will also be collected upon observation of any severe hypersensitivity reaction i.e., severe hypersensitivity reaction and anaphylaxis.

^m A single blood sample for pharmacogenomic analysis will be collected at visit 2, before study drug administration from patients who consent to this procedure. A separate informed consent form for pharmacogenomic sampling must be signed by the patient.

ⁿ Patients will respond first to the PHQ-2. They will respond to questions 3 through 9 (unique questions) of the PHQ-9 only if PHQ-2 is positive.

^o The eC-SSRS Baseline/Screening version will be completed at visit 1 and the eC-SSRS Since Last Visit version will be completed at all other visits.

^p Inquiries about adverse events will be made before and after study drug administration. Post-dose inquiries will be made before the patient leaves the study center.

Clinical Study Protocol with Amendment 01

⁹ Patients will be assessed for severe hypersensitivity/anaphylaxis reaction during and after administration of the IMP. Oxygen saturation and respiratory rate will be measured in cases of suspected anaphylaxis and severe hypersensitivity. See further details in [Appendix S](#).

ADA=anti-drug antibodies; β -HCG=beta human chorionic gonadotropin; ECG=electrocardiogram; eC-SSRS=electronic Columbia-Suicide Severity Rating Scale; EOT=end of treatment; EQ-5D-5L=EuroQol-5 Dimension, 5 response level version; FSH=follicle-stimulating hormone; HIT-6=6-item Headache Impact Test; IMP=investigational medicinal product; MIDAS=Migraine Disability Assessment; MSQOL=Migraine-Specific Quality of Life; PGIC=Patient Global Impression of Change; PHQ-2=2-item Patient Health Questionnaire; PHQ-9=9-item Patient Health Questionnaire; V=visit;; WPAI=Work Performance and Activity Impairment.

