4.2. Patient Exclusion Criteria

Patients will be excluded from participating in this study if they meet any of the following criteria:

- a. At the time of screening visit, patient is receiving any preventive migraine medications, regardless of the medical indication (as defined in [Appendix H](#)) for more than 5 days and expects to continue with these medications.
- b. Patient has received onabotulinumtoxinA for migraine or for any medical or cosmetic reasons requiring injections in the head, face, or neck during the 3 months before screening visit.
- c. The patient uses medications containing opioids (including codeine) or barbiturates (including butalbital/aspirin/caffeine [Fiorinal[®], Actavis plc], butalbital/paracetamol/caffeine [Fioricet[®], Cardinal Health], or any other combination containing butalbital) on more than 4 days during the run-in period for the treatment of migraine or for any other reason.
- d. The patient has used an intervention/device (eg, scheduled nerve blocks and transcranial magnetic stimulation) for migraine during the 2 months prior to screening.
- e. The patient uses triptans/ergots as preventive therapies for migraine.
- f. Patient uses non-steroidal anti-inflammatory drugs (NSAIDs) as preventive therapy for migraine on nearly daily basis for other indications. Note: Low dose aspirin (eg, 81 mg) used for cardiovascular disease prevention is allowed.
- g. The patient suffers from unremitting headaches, defined as having headaches for more than 80% of the time he/she is awake, and less than 4 days without headache per month. Daily headache is acceptable if patient has headaches 80% or less of the time he/she is awake on most days.
- h. The patient has a clinically significant hematological, cardiac, renal, endocrine, pulmonary, gastrointestinal, genitourinary, neurologic, hepatic, or ocular disease that, in the opinion of the investigator, could jeopardize or would compromise the patient's ability to participate in this study.
- i. Evidence or medical history of clinically significant psychiatric issues that, in the opinion of the investigator, could jeopardize or would compromise the patient's ability to participate in this study including major depression, panic disorder, or generalized anxiety disorder, any suicide attempt in the past or suicidal ideation with a specific plan the past two years prior to screening or current suicidal ideation as measured by eC-SSRS.

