- perform physical examination, including height and weight
- perform 12-lead ECGs in triplicate
- perform vital signs measurement
- perform beta human chorionic gonadotropin (β -HCG) serum pregnancy test (for women of child-bearing potential)
- perform FSH for postmenopausal women only
- inform patients of study restrictions and compliance requirements
- complete eC-SSRS

Patients who meet all inclusion and none of the exclusion criteria will be given an electronic headache diary device and will be trained in its use and compliance requirements on the day of screening. Patients will complete electronic headache diary entries about the previous day daily beginning on day -27 (visit 1) through the EOT/early withdrawal visit (visit 8).

2. Procedures Before Administration of Investigational Medicinal Products (Baseline Visit 2, Day 0+3 Days)

Patients who meet all inclusion and none of the exclusion criteria at visit 1 will continue to visit 2 (week 0), when baseline assessments will be conducted.

The following procedures will be performed at visit 2:

- review inclusion and exclusion criteria
- assign randomization/treatment numbers and enter in CRF
- perform clinical laboratory tests (serum chemistry, hematology and coagulation, urinalysis)

- perform physical examination, including weight
- perform 12-lead ECGs in triplicate
- perform vital signs measurements
- perform urine pregnancy test (women of child bearing potential only)
- review study compliance
- review electronic headache diary
- obtain blood samples for plasma concentration of IMP prior to dosing
- obtain a blood sample for serum ADA assay prior to dosing
- obtain blood collection for serum, plasma, and RNA biomarker analysis
- obtain urine sample for biomarker analysis
- collect a saliva sample for biomarker analysis
- obtain blood samples for pharmacogenetics before study drug administration from patients who consent to this procedure
- complete HIT-6
- complete the MIDAS
- complete the PHQ-2/ PHQ-9. Patients will respond first to the PHQ-2. Patients will respond to questions 3 through 9 (unique questions) of the PHQ-9 only if PHQ-2 is positive.
- complete the MSQOL questionnaire
- complete the EQ-5D-5L questionnaire
- complete the WPAI questionnaire
- inquire about adverse events and health care resource utilization
- inquire about concomitant medication

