- complete HIT-6
- complete MIDAS
- complete PHQ-2/ PHQ-9. Patients will respond first to the PHQ-2. Patients will respond to questions 3 through 9 (unique questions) of the PHQ-9 only if PHQ-2 is positive.
- complete MSQOL questionnaire
- complete EQ-5D-5L questionnaire
- complete PGIC scale
- complete WPAI questionnaire
- complete eC-SSRS
- inquire about adverse events and health care resource utilization
- inquire about concomitant medication
- assess hypersensitivity and anaphylaxis

5. Procedures for Follow up Period (Week 46, Visit 9, Day 320±15 Days)

The following procedures and assessments will be performed at the follow up visit (visit 9):

- Perform vital signs measurements
- obtain a blood sample for serum ADA assay
- inquire about adverse events and health care resource utilization
- inquire about concomitant medication

6. Procedures for Unscheduled Visits

An unscheduled visit may be performed at any time during the study at the patient's request and as deemed necessary by the investigator. The date and reason for the unscheduled visit will be recorded on the CRF as well as any other data obtained from procedures and assessments.

Procedures performed during unscheduled visits include:

- review electronic diary data
- review study compliance
- perform vital signs measurements
- inquire about adverse events and health care resource utilization

- inquire about/review concomitant medications
- complete the eC-SSRS Since Last Visit version

Other procedures and assessments may be performed at the discretion of the investigator.

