8.9. Electronic Columbia-Suicide Severity Rating Scale

The eC-SSRS will be used to assess the patient's suicidal ideation (severity and intensity) and behavior ([Posner et al 2011](#)). The eC-SSRS 'Baseline/Screening version' will be completed by the patient at visit 1 (screening), and the eC-SSRS 'Since Last Visit version' will be completed by the patient at months 1, 2, 3, 4, and 5, and at the end of treatment visit.

The results from the eC-SSRS will be listed.

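### Table 2's footnote and the visit schedule disagree on the eC-SSRS at visits 2 and 9, so no reading is scheduled between screening and the first dose 28 to 31 days later

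*Protocol*

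**What the plan says.** Footnote o to Table 2 (Protocol 3.4) gives the Baseline/Screening form to visit 1 and adds that "the eC-SSRS Since Last Visit version will be completed at all other visits". Taken literally, this covers visits 2 to 9.

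The eC-SSRS row of the same table is marked at visit 1 and at visits 3 to 8, and is blank at visits 2 and 9. Appendix B agrees with the row. It lists the instrument at screening, at visits 3 to 8 and at unscheduled visits, but neither in the pre-dose or post-dose lists for visit 2 nor in the list for visit 9. SAP 8.9 puts the Baseline/Screening form at visit 1 and says the later form "will be completed by the patient at months 1, 2, 3, 4, and 5, and at the end of treatment visit". Protocol 7.10 adds no timing of its own and refers back to Table 2.

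Visit 2 is the day of randomisation and first dose, and Table 2 and Appendix B both call for inclusion and exclusion criteria to be reviewed again then. One limb of exclusion criterion i (Protocol 4.2) is "current suicidal ideation as measured by eC-SSRS". Suicidal ideation and behaviour measured by the eC-SSRS is a named secondary safety endpoint (Protocol 2.1, SAP 1.1).

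**The concern.** Two things depend on the missing visit 2 reading.

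**Eligibility.** Criterion i turns on ideation being current, by a named instrument. On the day the criteria are re-reviewed, the latest scheduled result from that instrument is about four weeks old. Laboratory tests, physical examination, ECG, vital signs and a pregnancy test are all done at screening and again at visit 2; the eC-SSRS is not.

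**Dating of positives.** The first form after screening is at visit 3, and the first dose falls between the two. A positive at visit 3 cannot be placed before or after dosing from the forms alone. Protocol 7.1.2 counts events as treatment-emergent only after the first dose, so the distinction matters to anyone reading the listing, case by case.

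The wording conflict is also a practical problem. A site that follows the footnote and a site that follows the row would collect different data at visits 2 and 9.

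**Working it through.** **Step 1: the visits each source gives for the Since Last Visit form.** SAP months 1 to 5 correspond to visits 3 to 7, and end of treatment to visit 8.

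| Source | Visits | Scheduled forms after screening |
|---|---|---|
| Table 2 footnote o, literal reading | 2 to 9 | 8 |
| Table 2 row | 3 to 8 | 6 |
| Appendix B | 3 to 8 | 6 |
| SAP 8.9 | 3 to 8 | 6 |

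The row, Appendix B and SAP 8.9 agree with one another. They differ from the literal footnote at exactly two visits, 2 and 9. Because three sources agree, the blank cells are not an artefact of how the table was extracted.

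**Step 2: the intervals.** Inputs from Table 2: visit 1 at week -4, taken as day -28 for a 28-day run-in; visit 2 at day 0 with a window of +3 days; visit 3 at day 28 with a window of ±3 days.

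- Screening form to first dose: 0 + 28 = 28 days, up to 3 + 28 = 31 days. This reproduces the planned run-in of four weeks. If screening is counted as day -27, when diary entries begin, the range is 27 to 30 days.
- Screening form to the next scheduled form, at visit 3: 25 + 28 = 53 days, up to 31 + 28 = 59 days; nominally 28 + 28 = 56 days.
- Share of the nominal interval before dosing: 28 / 56 = 50%. This is a share of time, not of events.

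**Step 3: what the visit 3 form covers.** The documents do not reproduce the form's look-back instruction, so there are two cases.

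- If it looks back to the previous visit (visit 2), no scheduled eC-SSRS covers the 28 to 31 days of run-in.
- If it looks back to the previous form (visit 1), coverage is complete, but one answer spans both pre-dose and post-dose time.

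**Step 4: effect on the analysis.** SAP 4.2 takes the last value before the first dose as baseline for variables without a specific rule. For the eC-SSRS that is the screening form. SAP 8.9 provides for a listing only, with no test and no change from baseline. No p-value, interval or sample-size figure depends on the visit 2 cell.

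**The case against.** The strongest reply is that footnote o is about which version of the form to use, not when. It is attached to the eC-SSRS row, so its reference to other visits can fairly be read as the other visits ticked in that row. The literal reading would also require the form at visit 9, which is just as blank. This stands: the documents do not show that a visit 2 assessment was intended and then dropped, and a reader should not infer that. It does not remove the conflict, because the words are unqualified. Nor does it change the intervals above, which follow from the row itself.

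Three further replies have force.

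- *Criterion i can still be applied.* It fixes no day for the reading, and one of its other limbs is anchored to screening. Appendix B sends patients on to visit 2 once they qualify at visit 1. Criteria g and k need run-in diary data, so the visit 2 review has a purpose without a new eC-SSRS. It would therefore be too strong to say that the criterion is unusable at visit 2. What is missing is a recent result from the instrument it names.
- *The endpoint has a baseline.* It does, at screening. A reader might infer that there is none, and SAP 4.2 shows otherwise. That baseline does not date an event arising between visits 1 and 3.
- *Other information exists.* Adverse events are recorded from consent, with onset dates (Protocol 7.1.2), and are asked about before dosing at visit 2. The PHQ-2, extended to the PHQ-9 if positive, is completed then too, and any unscheduled visit includes an eC-SSRS. These may date some cases. They do not replace the instrument named in criterion i, and unscheduled visits do not cover every patient.

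**Conclusion.** The inconsistency is real and concerns visits 2 and 9. Its consequence at visit 2 is a gap of 28 to 31 days between the only scheduled pre-dose reading and the first dose, and of 53 to 59 days between the first and second scheduled readings, with dosing in between. These figures assume screening at day -28 and visits within the Table 2 windows. The gap is built into the schedule for every patient, planned at about 804, but that is the enrolment target and not a count of patients harmed or misclassified.

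A reader might infer from the 50% share of time that about half of new positives at visit 3 began before any study drug. The documents do not support that. It would need onset to be uniform over the interval and the form to look back to screening. The plan establishes neither, and it gives no event rate from which a number could be derived. Onsets during run-in also precede randomisation, so they should fall similarly across the three groups. The problem is dating individual cases, not a bias between arms.

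No inferential analysis changes. The effect is limited to how recent the eligibility reading is and to how individual positives in the listing are interpreted.

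**What to change.** Reconcile footnote o, the Table 2 row, Appendix B and SAP 8.9 so that they give the same visits, and deal with visits 2 and 9 explicitly. The documents do not settle which schedule was meant. There are two ways to make them agree:

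- Reword footnote o so that it refers only to the visits marked in the row. This costs one sentence, but the run-in gap stays.
- Schedule the Since Last Visit form at visit 2, before randomisation and dosing. This agrees with the footnote at that visit, gives criterion i a same-day reading and closes the run-in gap. It costs one more short electronic questionnaire at a visit that already has six (HIT-6, MIDAS, PHQ-2/PHQ-9, MSQOL, EQ-5D-5L, WPAI), plus one cell in Table 2 and one line each in Appendix B and SAP 8.9. No extra visit is needed. Visit 9 would still need its own decision.

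In either case, SAP 8.9 should state the period the visit 3 form covers, and the listing should flag positives whose onset may precede the first dose. This takes two sentences in the SAP and one flag in the listing.
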